# **1.4 Anticoagulant Therapy**

In the UK, evidence based guidelines provide recommendations to practitioners to support pharmacotherapeutic decision making. These are summarised in the sections below.

<sup>\*\* This study is not designed to monitor the safety and use of rivaroxaban in this group of off-label surgical patients. However since there is a need to inform on off-label use in non-orthopaedic medical conditions requiring anticoagulation, data from any patients within this latter category will be eligible for inclusion and evaluated as part of the secondary objective (ii) in Section 2.2.2

# 1.4.1 Atrial Fibrillation

For the diagnosis and management of patients with AF who are either post-stroke, or have had a TIA the following standard pharmacotherapeutic treatments are recommended:

- warfarin should be administered as the most effective thromboprophylactic agent
- aspirin or dipyridamole should not be administered as thromboprophylactic agents unless indicated for the treatment of comorbidities or vascular disease. [21]

# 1.4.2 DVT/PE

A choice of low molecular weight heparin (LMWH) or fondaparinux should be offered to patients with confirmed proximal DVT or PE, taking into account comorbidities, contraindications and drug costs with the following exceptions:

- For patients with severe renal impairment or established renal failure (estimated glomerular filtration rate [eGFR] <30 ml/min/1.73 m^2) offer unfractionated heparin (UFH) with dose adjustments based on the APTT (activated partial thromboplastin time) or LMWH with dose adjustments based on an anti-Xa assay.
- For patients with an increased risk of bleeding consider UFH.
- For patients with PE and haemodynamic instability, offer UFH and consider thrombolytic therapy.

The LMWH, fondaparinux or UFH should be started as soon as possible and continued for at least 5 days or until the international normalised ratio (INR) (adjusted by a vitamin K antagonist [VKA]) is 2 or above for at least 24 hours, whichever is longer.[22]

The Scottish Intercollegiate Guidelines recommend that after the first episode of limb deep vein thrombosis, continuation of anticoagulation with an oral anticoagulant (warfarin) is required as maintenance treatment. The aim is to minimise the risks of PE, recurrent DVT and post thrombotic syndrome (PTS) [23]

The British guideline on oral anticoagulation with warfarin recommends that:

- first episodes of VTE should be treated with an INR target of 2.5 the target range should not be lowered for patients who require anticoagulation beyond 3 months
- recurrent VTE whilst anticoagulated and within the therapeutic range should be managed by increasing the INR target to 3.5

• patients with proximal DVT or PE should be treated for at least 3 months to prevent extension of thrombus and recurrence. [24]

## 1.5 Considerations in initiating anticoagulation treatment, stroke and bleeding risk

For this study, it is important to capture information on a patient's stroke and bleeding risk score as derived from information within existing medical records relating to index date and end of observation, so that any changes in risk of either can be examined in relation to changes in factors associated with clinical condition.

The CHADS2 classification scheme is a clinical prediction rule (an acronym for Congestive heart failure, Hypertension, Age  $\geq$ 75 years, Diabetes mellitus, and prior Stroke or transient ischemic attack) that estimates the risk of stroke in patients with non-rheumatic atrial fibrillation.[25;26] Its use is advocated by the National Institute for Health and Clinical Excellence (NICE) to determine whether or not antithrombotic therapy should be initiated based on patient-specific stroke risk.[27] The classification scheme assigns a score (0 to 6; one point each for Congestive heart failure, Hypertension, Age  $\geq$ 75 years, Diabetes mellitus and two points for prior Stroke or transient ischemic attack) based on the number of risk factors an individual patient has; a high CHADS2 score corresponds to a greater risk of stroke such that a score of 2 and above indicated the need for oral anticoagulation therapy, while a low CHADS2 score corresponds to a lower risk of stroke, whereby other risk modifiers should be considered.

To complement the CHADS2 score, by the inclusion of additional 'stroke risk modifier' risk factors, the CHA2DS2-VASc score has been proposed. [25;26;28] These additional non-major stroke risk factors include age 65-74, female gender and vascular disease. In the CHA2DS2-VASc score, 'age 75 and above' also has extra weight, with 2 points.

In clinical practice, bleeding risk assessment should be performed prior to initiation of oral anticoagulation therapy. A validated bleeding risk score which is included within the European Society of Cardiology (ESC) Guideline for management of AF patients is the HAS-BLED (Hypertension, Abnormal renal/liver function, Stroke, Bleeding history or predisposition, Labile International Normalized Ratio, Elderly, Drugs/alcohol concomitantly) bleeding risk schema, whereby a score of  $\geq$ 3 indicates "high risk" and some caution and

regular review of the patient is needed. Note that knowledge of INR control is needed to assess the 'labile INR' criterion; otherwise for a non-warfarin patient, this scores zero.

In the UK, a NICE clinical guideline is available which outlines assessment of risks of VTE and bleeding in medical patients admitted to hospital. [29] It advocates a form of benefit risk assessment of offering VTE prophylaxis to medical, surgical and /or patients with trauma balanced against risk of VTE and bleeding. It also states that choice of pharmacological VTE prophylaxis should be based on local policy, clinical condition and patient preference. Thus it is important to examine whether the likely hierarchical clustering of patients –by region geographically and by medical institution has any impact on either bleeding risk assessment or incidence of haemorrhage.

# 2.0 AIMS AND OBJECTIVES OF STUDY

## 2.1 Overall aim:

To monitor the short-term (12 weeks) use and safety profile of rivaroxaban prescribed to newuser adult patients (i.e. rivaroxaban naïve who may or may not be antithrombotic therapy naïve) for the prevention of stroke and systemic embolism in adult patients with non-valvular atrial fibrillation, the treatment of DVT, PE, and the prevention of recurrent DVT and PE in adult patients, requiring anticoagulation under normal conditions of use in the secondary care hospital setting. In addition since it is desirable to put these observations into context and characterise a population treated with existing anticoagulant treatment to allow the variation in determinants of treatment choices to be examined in relation to risk, a similar number of evaluable patients receiving alternative anticoagulant therapy will be monitored in order to inform on the adoption of rivaroxaban into clinical practice.

## 2.2 Specific objectives:

## 2.2.1 The primary objective

Its purpose is to provide timely information on:

(i) Estimation of the cumulative incident risk (separately) of the following important identified risk for rivaroxaban users which is:

• Haemorrhage within gastrointestinal and urogenital organ sites (which meets the criteria for a major bleed) and all intracranial sites (Table 2))

## 2.2.2 Secondary Objectives

These are given below. Their purpose is to provide timely information on:

Version 40 20/11/2014 REC Ref 12/SC/0592

(i) Prescriber and cohort accrual and the type of prescriber responsible for, and the setting of initiation of treatment with either rivaroxaban or alternative anticoagulant therapy.

(ii) Prevalence of non-clinical reasons for prescribing, prognostic health factors and clinical risk factors for haemorrhage as reported in medical charts for patients undergoing anticoagulation with either rivaroxaban or alternative anticoagulant therapy in the secondary care hospital setting and the treatment programme they received to advance the understanding of the patient population prescribed rivaroxaban in actual clinical practice in the secondary care hospital setting

(iii) Changes of health profile of patients, assessment of adherence, plus any alterations of the treatment programme during the 12 week observation period, as recorded in medical charts.(iv) To quantify the risk of:

(a) (separately) haemorrhage within gastrointestinal and urogenital organ sites (which meets the criteria for a major bleed) and all intracranial sites for contextual anticoagulant therapy cohort

(b) all major bleeding specified in primary objective for both rivaroxaban and contextual anticoagulant therapy cohort (as composite)

(c) (separately) haemorrhage (major bleeding according to Table 2) within critical organ sites other than specified in primary objective for both rivaroxaban and contextual anticoagulant therapy cohort

(d) all major and clinically relevant non-major bleeds (as a composite outcome)

(e) thromboembolic complications (incident and recurrent)

(f) other†† events including special outcomes of interest (severe hepatic failure and abnormal LFTs above 3x ULN) as recorded in medical charts during the 12 week observation period and, if number of reports are sufficient, in patient subgroups of special interest, including:

- reported indications
- elderly (>= 65 years)‡‡, other contraindicated or special groups (e.g. pregnant and breastfeeding women, patients with concurrent significant renal or hepatic impairment; patients with known VTE and/or haemorrhagic risk factors e.g. congenital or acquired bleeding disorders, uncontrolled severe arterial

<sup>†† Other than major and clinically relevant non major bleeding outcomes, or thromboembolic complications (recurrent or incident)

<sup>‡‡ Children and adolescents aged less than 18 years of age will be excluded from the SCEM study. Since this is important missing information, data on this special population will be captured within the complementary M-PEM, if reported.

hypertension, active ulcerative gastrointestinal disease) and off-label groups (patients with other non-orthopaedic medical conditions)

 concomitant use of medications that are contraindicated or to be used with caution (e.g. CYP3A4 inducers/inhibitors, P-gp inhibitors, anticoagulants, aspirin, nonsteroidal anti-inflammatory drugs (NSAIDs), oral steroids, hormone and oral contraception therapy and platelet aggregation inhibitors)

## 2.2.3 Exploratory objectives (for rivaroxaban only)

The specific objectives that follow are all exploratory. The purposes of these objectives are:

(i) Where possible, to quantify the incidence of other important identified and potential risks (not mentioned in objective 2.2.1), other frequently and rarely reported adverse events as recorded in the medical charts and to identify previously unrecognised ADRs

(ii) To describe clinical features and management of cases of overdose, major bleeding (according to pre-specified definition (Table 2), VTE events indicating failure of anticoagulation and management of homeostasis during surgery as recorded reporting the medical charts in the first 12 weeks after treatment initiation in the cohort exposed to rivaroxaban.

#### Table 2. Haemorrhage outcomes[30]

# A major $\dagger$  bleeding event will be defined using ISTH criteria (21) as clinically overt bleeding that is associated with:

- A fall in haemoglobin of 2 g/dL or more, or
- A transfusion of 2 or more units of packed red blood cells or whole blood, or

• A critical site: intracranial, intraspinal, intraocular, pericardial, intra-articular, intramuscular with compartment syndrome, retroperitoneal, or

• A fatal outcome

A clinically-relevant non-major bleeding event is defined as an overt bleeding event not meeting the criteria for a major bleeding event, but associated with medical intervention§§, unscheduled contact (visit or telephone call) with a physician, (temporary) cessation of study drug treatment, or associated with discomfort for the subject such as pain or impairment of activities of daily life.

#### Examples of non-major clinically relevant bleeding events are:

• Epistaxis if it lasts for more than 5 minutes, if it is repetitive (i.e., 2 or more episodes of true bleeding, i.e., no spots on a handkerchief, within 24 hours), or leads to an intervention (packing, electrocautery, etc.)

• Gingival bleeding if it occurs spontaneously (i.e. unrelated to tooth brushing or eating), or if it lasts for more than 5 minutes

- Haematuria if it is macroscopic, and either spontaneous or lasts for more than 24 hours after instrumentation (e.g., catheter placement or surgery) of the urogenital tract
- Macroscopic gastrointestinal haemorrhage: at least 1 episode of melena or haematemesis, if clinically apparent
- Rectal blood loss, if more than a few spots
- Haemoptysis, if more than a few speckles in the sputum, or
- Intramuscular hematoma
- Subcutaneous hematoma if the size is larger than 25 cm 2 or larger than 100 cm^2 if provoked
- Multiple source bleeding events

† The three organ sites included in the primary objective are gastrointestinal and, urogenital (which meet the criteria for major bleed) and intracranial. Case definition will be confirmed by project steering committee prior to patient recruitment.

<sup>§§ Such as: Surgical or endoscopic intervention; decompression of a closed space to stop or control the event; protamine sulphate administration

## 3.0 ETHICAL CONSIDERATIONS

All studies carried out by at the DSRU will be conducted in accordance with national and international guidelines. [31;32] For this cohort study, ethics approval via IRAS (integrated research application system) in the UK will be required. Participating specialist HCPs will be asked to provide patients with documentation (with a unique study reference code). Patient study documentation will include an patient information sheet about the study which will describe that their secondary care medical charts will be accessed during the time-frame of active study data collection by the specialist HCP and/or DSRU research staff in order to extract exposure and outcome data relevant to the 12 week observation period, \*\*\* and also that their primary care medical charts may be accessed (*contact details to be provided on the consent form*), if they are discharged to the care of their GP within the 12 week observation period. It will also provide contact details of the DSRU study team if they have any questions.

Specialist HCPs will provide patients with a consent form so that patients can consider and give consent for their participation within this project. The consent form will stress confidentiality, that no specific details of their treatment will be released to external parties, that the patient may withdraw consent at any time by contacting either the specialist HCP or the DSRU study research team directly, and that the patient will not be asked to attend clinics more than usual or undergo any additional treatment or questioning. The consent form will also request information to be provided on patient ethnicity, current marital status, current employment status, smoking and alcohol use. This is optional and will be used to inform on representativeness of study cohort. Three signed copies are required. Those patients who wish to inform the DSRU immediately of their decision will give the signed consent form to the specialist HCP. They in turn will send the original to the DSRU, retain one copy for their records and issue a copy to the patient. Where a patient is unable to sign the consent form (e.g. because of weakness of the dominant hand following stroke), consent will be confirmed orally in the presence of a witness (an individual other than the person taking consent) who will sign the consent form on behalf of the participant.

For those patients who wish to have a further opportunity to reflect on their participation, the specialist HCP will ask the patient to complete a 'consent to contact' form, which will enable DSRU study research staff to contact the patient through their preferred route of contact (surface post, email, or telephone) after a period of at least two days to obtain consent. This

\*\*\* The exception will be if a female patient becomes pregnant, the outcome of the birth will be requested.
Version 40 20/11/2014 REC Ref 12/SC/0592 22

will be the only point at which DSRU research staff will contact the eligible patients directly. If the patient agrees to participate, they will sign the consent form, retain a copy and send the original and one further copy via surface mail to the DSRU study coordinating centre, or, if preferred, to the specialist HCP (who will then submit the original form to the DSRU). Receipt of the signed consent to contact form or the fully completed consent form (if patient provides immediate consent) by the DSRU study team should be within 4 weeks after index date, if possible.

In addition, within the same time frame, the specialist HCP will be asked to summarise selected data from the medical charts (non-clinical reasons for prescribing, demographic and treatment details) using a simple questionnaire (anonymised using the patient's allocated study reference number) and send these data to the DSRU coordinating centre either through a secure electronic website, or via surface mail.

#### 3.1 Consent for patients without mental capacity

We wish to include patients who do not have mental capacity and who are therefore unable to consent for themselves. This would include patients who have had a stroke, have cognitive impairment, dementia and/or learning difficulties. Due to the nature of the indication for use, many patients with these conditions may be prescribed rivaroxaban and these are patients who may be unable to consent for themselves but are still at risk of adverse events and therefore should be included. Exclusion of patients with mental incapacity would mean exclusion of a group of potentially high risk patients.

For potential patients who lack mental capacity to consent to research, a medically qualified member of the care team will identify a personal consultee to approach and discuss the study with. This will be a person who is in a position to advise on the wishes and feelings of the potential patient in relation to taking part in this research project. It is anticipated that the personal consultee would be a family member or friend. In the situation where no family member or friend is willing and able to act as a consultee, a nominated consultee will be sought following the local arrangements in situ. This will be a person who has no connection with the project and who is willing to be consulted about the participation of the person who lacks capacity in the research project. In the situation where consent is being sought out of hours and there is no nominated consultee available, the process can wait until a suitable person is available.

The identified consultee will be provided with a consultee information sheet (there will not be a separate information sheet for the nominated consultee, if they wish to view a copy then they can request a copy of the personal consultee information sheet) and will also have an opportunity to ask

questions. The consultee will then be asked to complete a consultee declaration form if they believe the patient would have no objection to taking part in the study.

If a patient regains capacity during their participation in the study, they will be informed about the study, given a patient information sheet and asked to provide their own consent in the normal way. If a patient does not wish to continue in the study, they will be withdrawn.

#### 4.0 METHODS

#### 4.1 Study Design & Time frame

This study will be a registry-based observational, population-based cohort study with an internal contextual cohort utilising the technique of cohort event monitoring to study the short-term (up to 12 weeks) safety profile and use of rivaroxaban prescribed by specialist HCPs in the secondary care hospital setting in the immediate post-marketing period for the licence extension. Twelve weeks observation is regarded as a period of time sufficient for data from all relevant patient populations (which informs on any post start of observation health events related to short-term exposure that they might have experienced) to be recorded in the patient's medical charts by specialist HCP. Randomisation will not be required. Once the pharmacotherapeutic treatment decision has been made, and either rivaroxaban or the alternative anticoagulation therapy prescribed as the most appropriate treatment based on clinical need, a patient will be invited to participate in the study and consent obtained for access to information from medical charts (see section 3.0).

Study start is defined as the date that the first patient is recruited into the study, which is anticipated to begin May 2013 (*exact date to be confirmed*) and continue for a maximum of 36 months, or until the target sample size for both cohorts has been achieved (whichever is the soonest); see section 4.2. The final cohort sizes, period of observation and the duration of the SCEM study will be dependent on the level of prescribing of rivaroxaban by specialist HCPs in England and Wales (see section 4.2). Data collected during later time periods can be compared with earlier periods to identify any trends that may be emerging. Slow uptake may impact on the ability to meet the study objectives; in this instance the need to continue data collection, extend the observation period and the feasibility of study completion within the proposed time frame should be open to re-evaluation.

Period of observation for analyses will commence from index date (i.e. actual start date of anticoagulant treatment, not the date first seen by the specialist) and continue for 12 weeks (or less if patient discontinues to be under the care of the specialist HCP; to be established via the 12 week end of observation questionnaire) in order to allow for detection of outcomes associated with oral anticoagulant treatment initiation as recorded in medical charts. This study will also collect information on exposure to any other medicines (including those given as part of acute care management within the four calendar weeks prior to index date) as recorded in medical charts in order to explore impact of those treatments on outcomes of interest. Since patient care is likely to be shared between secondary and primary care for most patients during the 12 week observation period, the patient's GP will be contacted††† to complete a simple questionnaire to collect any information on outcomes of interest that have been recorded in the patient's medical charts held in primary care during the 12 week observation period to minimise under-reporting on selected outcomes. Where additional outcomes are identified that have not be reported by the initiating prescriber, these will be followed-up with the GP to ascertain further information.

## 4.2 Sample size

# 4.2.1 Sample size for primary outcome (haemorrhage – within intracranial, gastrointestinal and urogenital critical organ sites) where expected cumulative incidence is known

Where studies, such as clinical trials, have already estimated the impact of the exposure on the outcome of interest, the one objective of this observational study is to be able to estimate the measure of frequency so that it lies within a range (margin of error) close to the estimate from the RCT, assuming this represents the true value. Ideally this margin of error (also called precision) should be as narrow as possible, so that the frequency is estimated as precisely as possible [33], for example the margin of error is equal to half the width of the confidence interval. for the frequency estimate As such, in this study it is more appropriate to choose a sample size that will yield a confidence interval of a predefined width for those identified risks defined within the primary outcome which are of greatest clinical and medical importance i.e. major bleeding outcomes (Section 2.2.1). Table 3 displays the samples sizes (95% confidence intervals) across a range of expected incidences and levels of precision.

<sup>††† Overlap of data collection between SCEM and M-PEM should minimise any under-reporting of events of interest associated with the primary objective. However due consideration should be given to a) possible nonresponse of GPs for the long-term M-PEM study that might arise from the GP's knowledge that the patient is participating in the SCEM and b) that some patients are managed by specialist GPs purely on an outpatient basis and thus may never be officially admitted to hospital. The emphasis must be made that the two studies are complementary and participation in both is highly desirable.

From rivaroxaban clinical trial data, the cumulative incidence of each of the primary outcome major bleeding events (GI, urogenital and intracranial) in patients taking rivaroxaban for DVT and prevention of recurrent DVT and PE over 12 weeks of treatment was approximately 0.2%, 0.1% and 0.0%, respectively. Since information on the reported incidence for intracranial major bleeding outcomes within the first 12 weeks of treatment is limited, the reported incidence of intracranial haemorrhage with enoxaparin/vitamin K antagonist (VKA) from RCTs of 0.1% within 12 weeks will be used as an estimate of the incidence of that event in this population for rivaroxaban. From clinical trial data, the cumulative incidence of the primary outcome major bleeding events was similar in patients taking rivaroxaban for PE (~0.3%). As such, we do not expect any difference in cumulative incidence of bleeding between PE and DVT patients.

The formula used to calculate the sample size based on an estimation of the proportion of patients who will experience major bleeding outcomes is[33]:

Sample size= 
$$3.84 \times p(1-p)$$
 \_where p= estimated proportion (cumulative incidence)  
(precision)

Thus in this population of patients taking rivaroxaban for the treatment of DVT and PE and prevention of recurrent DVT and PE, in order to estimate the expected (true) cumulative incidence of the primary outcomes of major bleeding (GI, urogenital and intracranial) of 0.4% (0.2%, 0.1% and 0.1%, respectively), within  $\pm 0.39\%$ , we would need a sample size of 1005 patients (Epi Info v6).

The cumulative incidence of each of the primary outcome major bleeding events (GI, urogenital and intracranial) in patients taking rivaroxaban for the prevention of stroke and systemic embolism in adult patients with non-valvular atrial fibrillation over 12 weeks of treatment was approximately 0.5%, 0.1% and 0.1%,‡‡‡ respectively. [5] Thus, in this population of patients taking rivaroxaban for the prevention of stroke and systemic embolism in adult patients with non-valvular atrial fibrillation, in order to estimate the expected (true) cumulative incidence of the primary outcomes of major bleeding (GI, urogenital and

<sup>‡‡‡ Approximate estimates of cumulative incidence in 12 weeks of treatment, based on steady increase in incidence over time and overall cumulative incidence from a median of 590 days treatment exposure (90/590\*N)

intracranial) of 0.7% (0.5%, 0.1% and 0.1%, respectively), within  $\pm -$  0.69%, we would need a sample size of 561 patients.

Thus, in summary, for this study, a minimum sample size of 1700 evaluable patients for rivaroxaban is desirable to ensure the minimum of 1005 and 561 patients is achieved for each of the two indications described above for each drug, based on ratio of 1:2 respectively, with 12 weeks observation period sufficient to estimate cumulative incidence of specified primary outcomes of interest with desired precision. A similar number of evaluable new user alternative anticoagulant therapy patients will be collected for the internal contextual cohort.

In this study, sample size has been calculated such that the study estimate of cumulative incidence of major bleeding within each indication should fall with a pre-specified proportion which is relative to the true value. There is no ideal precision which should be used when calculating sample size, so use of proportion as an indicator of relative precision ensures the margin of error remains appropriate to the estimated size of cumulative incidence of major bleeding events.

Table 3. Sample sizes of evaluable patients required to estimate the expected (true)
cumulative incidence of a specified adverse event with 95% confidence intervals of
different precisions (0.2% to 5%).

Incidence	Precision							
from RCT	0.20%	0.39%	0.50%	0.69%	1%	2%	3%	5%
(%)								
0.10	958	252	153	81	38	10	4	2
0.20	1913	504	307	161	77	19	9	3
0.30	2864	755	459	241	115	29	13	5
0.40	3812	1005	612	321	153	38	17	6
0.50	4755	1255	764	401	191	48	21	8
0.70	6631	1752	1067	561	267	67	30	11
0.80	7564	2000	1218	640	305	76	34	12
1.00	9418	2494	1519	798	380	95	42	15
2.00	18475	4926	3003	1579	752	188	84	30
3.00	27187	7296	4452	2342	1117	279	124	45
4.00	35566	9605	5866	3089	1473	369	164	59
5.00	43627	11854	7246	3818	1821	456	203	73

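### Section 4.2.1 sizes the study on the sum of three bleeding sites, but the primary objective estimates each site separately, with half-widths larger than the expected risk within each indication

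*Supplement*

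**What the plan says.** Section 2.2.1 sets the primary objective as "Estimation of the cumulative incident risk (separately) of the following important identified risk for rivaroxaban users", namely major GI bleeding, major urogenital bleeding and any intracranial bleeding. Section 2.2.2 places "all major bleeding specified in primary objective for both rivaroxaban and contextual anticoagulant therapy cohort (as composite") among the secondary objectives, as (iv)(b).

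Section 4.2.1 explains that precision may be read so that "the margin of error is equal to half the width of the confidence interval", and uses n = 3.84 p(1−p)/precision². For DVT/PE, p is the sum of the sites: "primary outcomes of major bleeding (GI, urogenital and intracranial) of 0.4% (0.2%, 0.1% and 0.1%, respectively"), with a margin of 0.39%, giving 1005. For AF, p is 0.7% (0.5%, 0.1% and 0.1%) with a margin of 0.69%, giving 561. It then describes 1700 rivaroxaban patients, chosen to secure those two minima, as "sufficient to estimate cumulative incidence of specified primary outcomes of interest with desired precision". It says that the size was set within each indication, and that "use of proportion as an indicator of relative precision ensures the margin of error remains appropriate" to the size of the incidence. Table 3 gives sizes for other incidences and margins, but the text names no target for any single site.

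Section 4.7.2 promises a 95% confidence interval without naming a method. It lists indication among the factors to stratify by where possible. It also adds a rule: if the observed incidence lies within the precision limits around the trial figure, the null hypothesis of no difference is not rejected.

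**The concern.** The quantity that was sized is a secondary outcome, while the claim of adequate precision is made for the primary ones. Adding the three risks raises p. On a relative scale that makes the target easier to reach than it is for any component, and two of the three components are expected at only 0.1%.

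Two things are at stake. First, a reader of the protocol would expect usable estimates of urogenital and intracranial bleeding within each indication, when the likely result is zero, one or two events. Second, the rule in 4.7.2 needs limits for whatever outcome it is applied to, and limits have been set only for the sum. Lending them to a rare site would let a severalfold excess pass as agreement with the trials, in a safety study requested by the regulator.

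**Working it through.** **Inputs (section 4.2.1).** DVT/PE: GI 0.2%, urogenital 0.1%, intracranial 0.1%, n = 1005, margin 0.39%. AF: GI 0.5%, urogenital 0.1%, intracranial 0.1%, n = 561, margin 0.69%. The factor 3.84 is 1.96², for 95% intervals.

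**1. The plan's figures reproduce, from the sums.**
- DVT/PE: 3.84 × 0.004 × 0.996 / 0.0039² = 1005.8 (stated 1005).
- AF: 3.84 × 0.007 × 0.993 / 0.0069² = 560.6 (stated 561).

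The chosen margins are 0.39/0.40 = 97.5% and 0.69/0.70 = 98.6% of the summed risk. These percentages are inferred; the plan does not state them.

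**2. Each site at the planned n.** Half-width = √(3.84 p(1−p)/n); chance of no events = (1−p)ⁿ.

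| Group, site | p | Half-width | Half-width / p | Expected events | Chance of none |
|---|---|---|---|---|---|
| DVT/PE, GI | 0.2% | 0.276% | 138% | 2.0 | 13% |
| DVT/PE, urogenital or intracranial | 0.1% | 0.195% | 195% | 1.0 | 37% |
| AF, GI | 0.5% | 0.584% | 117% | 2.8 | 6% |
| AF, urogenital or intracranial | 0.1% | 0.261% | 261% | 0.56 | 57% |

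Every half-width is inside the absolute margin for its group. Table 3 agrees: at those margins the sites need 504 and 252 (DVT/PE) and 401 and 81 (AF), all fewer than planned. But every half-width exceeds p, so every lower limit by this formula is below zero.

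**3. Pooling the indications.** With 1700 patients and an assumed 2:1 mix of DVT/PE to AF, GI risk is (2 × 0.2% + 0.5%)/3 = 0.30%. Its half-width is 0.26%, or 87% of p. A 0.1% site has half-width 0.15%, or 150% of p.

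**4. The sum, with exact (Clopper-Pearson) 95% intervals.** About 4 events are expected in each group (1005 × 0.004 = 4.02; 561 × 0.007 = 3.93).
- 4/1005: 0.11% to 1.02%, half-width 0.45% (stated 0.39%).
- 4/561: 0.19% to 1.82%, half-width 0.81% (stated 0.69%).

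**5. Exact intervals for single sites near the expected counts.**
- DVT/PE: 2/1005 gives 0.02% to 0.72%; 1/1005 gives 0.003% to 0.55%; 0/1005 gives 0% to 0.37%.
- AF: 3/561 gives 0.11% to 1.55%; 1/561 gives 0.005% to 0.99%; 0/561 gives 0% to 0.66%.

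**6. The decision rule with the composite margins lent to a 0.1% site.**
- DVT/PE: the upper limit is 0.1% + 0.39% = 0.49%. Four events in 1005 is 0.40%, four times the expected risk, and falls inside.
- AF: the upper limit is 0.1% + 0.69% = 0.79%. Four events in 561 is 0.71%, seven times the expected risk, and falls inside.

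If the true risk were 0.1%, the binomial chance of four or more events would be 1.9% in 1005 patients and 0.3% in 561.

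**The case against.** The best defence is that the only numerical precision in the plan is absolute. By the plan's own formula each site meets it with patients to spare, and Table 3 prints the numbers. That stands. A reader might infer from the mismatch that the stated precision fails for every primary outcome; on the absolute margins it does not. With exact intervals, too, the DVT/PE sites and the 0.1% AF sites stay inside. Only AF GI bleeding goes slightly over: half-width 0.72% at 3/561, against 0.69%.

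A reader might also scale the implied 97.5% and 98.6% down to the sites and conclude that the study needs about 2016 and 4035 patients (DVT/PE), or 787 and 3948 (AF). The documents do not set that requirement. They give no numerical proportion, and they attach the relative idea to major bleeding within each indication, not to each site.

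The objective in 2.2.1 is worded for rivaroxaban users without a split, and pooled GI bleeding does reach the implied relative precision. This limits the point for GI but does not rescue the 0.1% sites.

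Finally, one could argue that normal-approximation intervals would cover poorly at these counts. Section 4.7.2 names no interval method, and the formula in 4.2.1 is for planning, so that cannot be charged to the analysis.

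What the defence does not answer is the rationale in 4.2.1. An absolute margin of 0.39% around a risk of 0.1% is not in proportion to that risk, and proportion is the reason the section gives for its choice.

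**Conclusion.** The mismatch is real and the text needs correcting. The sizes 1005 and 561 belong to the within-indication sum, which is a secondary outcome, while the claim of desired precision is made for the separate primary outcomes. Within each indication the half-width for every site exceeds the expected risk (117% to 261% of p), so precision in proportion to the incidence is not achieved, whatever proportion up to 100% was meant. For the sum, the stated margins are optimistic by about one sixth against exact intervals (0.45/0.39 and 0.81/0.69). The decision rule has no valid limits for a single site.

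These results rest on the plan's own incidences, on the minimum group sizes and, for the pooled figures only, on an assumed 2:1 mix; section 4.2.1 gives the ratio in the opposite order to the counts. Splitting the full 1700 as 1133 and 567 changes little: GI half-widths become 130% and 116% of p.

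**What to change.** In 4.2.1:
- State that 1005 and 561 size the sum of the three sites within each indication.
- Replace the margins of 0.39% and 0.69% by the exact intervals expected at 4 events (0.11% to 1.02%; 0.19% to 1.82%).
- Add, for each site and indication, the expected events, the chance of none and an exact interval at the expected count.
- Reword the claim of desired precision to match.

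In 4.7.2:
- Name the interval method: Clopper-Pearson, or the Wilson score interval.
- Report the primary estimates by indication, as sized. A pooled figure may be added with the recruited mix shown.
- Do not apply the composite margins to single sites. Confine the rule to the sum, or give each site its own limits.

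Making the composite primary, with the sites as components, would also remove the mismatch, but it is optional.

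The cost is a change of wording and a less favourable stated precision. No extra patients are needed.
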